4.1.7.2 Handling of rescreened subjects

A rescreened subject is defined as a subject who fails the initial screening attempt and is then screened failed and rescreened under a new subject identifier. Successful rescreen subjects will not be counted as a screen failure. In case of rescreening, all the data (including that from the initial screening and rescreening) will be presented under the latest rescreened subject ID and will be used in summary tables, figures and listings. The exception is for demographic and baseline characteristics analyses, where the data collected under the latest rescreened subject ID will be used (e.g. age, date of diabetes mellitus diagnosis). For rescreened subjects, the original subject identifier(s) will also be presented in the demography listing for cross-linking purposes. Records from the initial screening attempt(s) will be flagged in AE, prior and concomitant medication, medical history, laboratory, and vital sign listings.

4.1.7.3 Handling of implausible glucose results

It was identified prior to Week 56 database lock during ongoing data review that there was an implausible FPG value recorded for one subject at their Day 1 visit. This was investigated and confirmed by the central laboratory and it was decided that the results will be used in the primary analysis.

A sensitivity analysis of the secondary efficacy endpoints for FPG excluding this result and any other outliers may be conducted post-Week 56 database lock, if deemed necessary.

4.1.8 Missing data

If not stated otherwise, no imputation of missing data will be done. Efforts will be made to follow the subjects and collect the data even after the subjects discontinue the treatment.

For the primary and secondary efficacy analysis based on laboratory data (i.e. HbA1c, FPG) missing data will be handled using multiple imputation, as described in Section 4.1.12. Approaches that will be used to handle missing data for other efficacy analyses will be described in the respective analysis sections.

Information regarding handling of missing or partial event or medication dates is provided in the Appendix (Sections 8.2 and 8.3).

4.1.9 Weighted analysis of covariance (ANCOVA)

In summaries of primary and secondary efficacy endpoints examining the change from baseline at Week t , an ANCOVA model of the differences between Week t and baseline measurements will be used, controlling for baseline value as a covariate, and treatment group (regimen) and randomisation strata as fixed effects. Only main effects of the randomisation strata will be included in the model. The model will have the following form:

$$D_{t,ijm} = \text{intercept} + \beta [Y_{0,ijm}] + \tau_j + \omega_m + \text{error}_{ijm}$$

where:

- $D_{t,ijm} = Y_{t,ijm} - Y_{0,ijm}$ = the Week t change from baseline of subject i in treatment group j and stratum m .
- $Y_{0,ijm}$ is the baseline measurement of subject i in treatment group j and in strata m ,
- $Y_{t,ijm}$ is the Week t measurement of subject i in treatment group j and in strata m ,
- β is the slope of $D_{t,ijm}$ regressing on the baseline measurement,
- τ_j is the mean effect of treatment group j ,
- ω_m is the mean effect of randomisation stratum m ,
- *Intercept*, β and τ_j are unknown parameters to be estimated from the data.

Weights will be used in the ANCOVA model to test the treatment regimens compared to placebo, $\mathbf{H}_{01}: \tau_{TR1} - \tau_{Pla} = 0$ and $\mathbf{H}_{02}: \tau_{TR2} - \tau_{Pla} = 0$.

The weight matrices to test hypotheses \mathbf{H}_{01} and \mathbf{H}_{02} are denoted by \mathbf{W}_1 and \mathbf{W}_2 respectively, defined as follows:

$$\mathbf{W}_1 = \text{Diag} \begin{bmatrix} \mathbf{1}_{1 \times n} \\ \mathbf{1}_{1 \times rn} \\ \mathbf{2}_{1 \times (1-r)n/2} \\ \mathbf{0}_{1 \times \frac{(1-r)n}{2}} \end{bmatrix} \quad \mathbf{W}_2 = \text{Diag} \begin{bmatrix} \mathbf{1}_{1 \times n} \\ \mathbf{1}_{1 \times rn} \\ \mathbf{0}_{1 \times \frac{(1-r)n}{2}} \\ \mathbf{2}_{1 \times (1-r)n/2} \end{bmatrix}$$

where r is the proportion of response (HbA1c < 7%), n is the number of subjects within an arm, and based on a 1:1:1 randomisation.

\mathbf{W}_1 : For the comparison of the low-dose/high-dose treatment regimen versus placebo (used for secondary endpoints), all dapagliflozin and saxagliptin subjects who had HbA1c < 7% at Week 12 and remained on the low-dose will be assigned a weight of 1. The dapagliflozin and saxagliptin subjects who had HbA1c \geq 7% at Week 12 and continued on the low-dose will be assigned a weight of 0. The dapagliflozin and saxagliptin subjects who had HbA1c \geq 7% at Week 12 and received the high-dose will be assigned a weight of 2. All subjects who do not undergo the second randomisation and all placebo subjects will be assigned a weight of 1.

\mathbf{W}_2 : For the comparison of the low-dose treatment regimen versus placebo (used for secondary endpoints), all dapagliflozin and saxagliptin subjects who had HbA1c < 7% at Week 12 and remained on the low-dose will be assigned a weight of 1. The dapagliflozin and saxagliptin subjects who had HbA1c \geq 7% at Week 12 and continued on the low-dose will be assigned a weight of 2. The dapagliflozin and saxagliptin subjects who had HbA1c \geq 7% at Week 12 and received the high-dose will be assigned a weight of 0. All subjects who do not undergo the second randomisation and all placebo subjects will be assigned a weight of 1.

For the comparison of overall drug treatment versus placebo (used for the primary endpoint analysis and some secondary endpoints) no weighting will be used (i.e. all treatment groups will be assigned a weight of 1).

It follows that parameters can be estimated with appropriate design and weight matrix by

$$\hat{\beta} = (X'WX)^{-1}X'WY \sim N(\beta, \Sigma)$$

such that $\hat{\beta} = [\hat{\beta}_{Intcpt} \quad \hat{\beta}_{Tr} \quad \hat{\beta}_{Base} \quad \hat{\beta}_{Strata}]^T$

and the design matrix for i -th subject $x_i = [1 \quad Trt \quad x_{baseline} \quad Y_{Strata}]$.

The model will provide least squares mean (LS mean) estimates and 2-sided 95% confidence intervals for mean changes from baseline within each treatment group (regimen) and differences in mean change from baseline between a treatment group (regimen) and placebo. Note that CIs will not be obtained directly from the model, but will be derived by combining the results obtained from running the ANCOVA model in each imputed data set, as described in Section 4.1.12.4. If there is no missing data for all treatment groups in the analysis at a visit, then the ANCOVA model will be run on the non-imputed data and no combining of results from each imputed data set is necessary.

Standardised model residuals will be used to examine model assumptions and to detect outliers and potentially influential observations. The "Influence Diagnostics" output produced by PROC MIXED and box plots of standardised residuals will be used to facilitate this diagnostic analysis. If influential outliers are present additional sensitivity analyses will be performed with the outliers excluded, in order to assess their impact on treatment (regimen) comparisons.

4.1.10 Proportion of subjects with a pre-defined characteristic (responders) at Week t

The proportion of subjects with a *pre-defined characteristic (responders)* at Week t will be analysed using a weighted or unweighted logistic regression when there are at least 5 responders by treatment group. For proportion of responders (e.g., meeting HbA1c criteria), estimates, confidence intervals, and tests will be obtained using a weighted or unweighted logistic regression. Odds ratios (and corresponding standard errors [SE]) representing the responder odds in the dapagliflozin/saxagliptin treatment group (or regimen) versus placebo group will be generated adjusted for baseline variable (e.g., adjustment for baseline HbA1c) and each randomisation stratification factor using the SAS LOGISTIC procedure.

The frequencies of response/non-response and the associated crude response rates (as percentages) will be presented by treatment group (or regimen). In addition, weighted or non-weighted adjusted percentages, standard errors, and 95% CIs for each treatment group (or regimen) will also be displayed. Adjusted odd ratio and corresponding 95% Log likelihood confidence interval, and p-values (uncorrected) will also be presented.

For the HbA1c responder endpoints, if there is no missing data for all treatment groups in the analysis at Week t, then the logistic regression model or Fisher's exact test will be run on the non-imputed data and no combining of results from each imputed data set is necessary.

In case of non-convergence because of sparse data subsequent backup models will be used in removing randomisation strata in sequential order and/or collapsing the randomisation strata of background medication as defined in Section 4.1. A subsequent back-up model in the order presented Section 4.1 will only be provided if the preceding back-up model does not converge.

When there are less than 5 responders in any treatment group, the unadjusted (and difference) proportions, weighted or non-weighted exact 95% confidence interval, and p-values from the weighted or unweighted Fisher's exact test (when applicable) will be provided.

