4.1.3 Descriptive summaries of categorical variables

Categorical data will be summarised for each treatment group or regimen as the number and percentage of subjects in each category. Percentages will be calculated out of the total number of subjects in the analysis set (and treatment group as appropriate) for the variable summarised.

Weighted proportions will be calculated as the weighted count of subjects with the event out of the total number of weighted subjects in the analysis set (and treatment group as appropriate).

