4.1.12.4 Combining multiple imputation results

Continuous endpoints

The analysis model will be evaluated in each of the imputed datasets, and the point estimates and SEs will be combined using Rubin's rules to produce valid global estimates with corresponding CIs and p-values. SAS MIANALYZE procedure will be used for this purpose.

Categorical endpoints

HbA1c will be categorised as $< 7\%$ (responders) or $\geq 7\%$ (non-responders) and will be derived from dichotomising the imputed continuous values of HbA1c.

A logistic regression (the SAS LOGISTIC procedure) will be used when there are at least 5 responders by treatment regimen. If there are less than 5 subjects in any treatment regimen, the Fisher's exact test will be used.

- If the logistic model is used, prior to applying Rubin's rules (as described in Section 4.1.12.4) the odds ratio and its SE will be log-transformed (as detailed below).

If Fisher's exact test is used, the final estimates for the proportion of responders, difference in proportion of responders and p-value will correspond to the median of these estimates across all imputed data sets.

Log-transformation of odds ratio estimates

Rubin's combination rules assume that the multiple imputation estimates are asymptotically normally distributed. However, the estimates of odds ratios follow a log-normal distribution. A log transformation can be used to normalise these estimates in order to be able to apply Rubin's combination rules, as follows:

- Obtain log-transformed odds ratio (OR) and SE from each imputed dataset
 $\log_OR = \log(OR)$
 $\log_OR_SE = \log(upper_CI) - \log(lower_CI) / (2 * 1.96)$
- Combine transformed estimates using MIANALYZE
- Back-transform combined estimates (ESTIMATE and STDERR are the results from PROC MIANALYZE):
 $Pooled_OR = \exp(ESTIMATE)$
 $Pooled_lower_CI = pooled_OR * \exp(-1.96 * STDERR)$
 $Pooled_upper_CI = pooled_OR * \exp(+1.96 * STDERR)$

The above code assumes that 95% CIs are used. If different width is required, the 1.96 multiple will need to be adjusted accordingly.

Further information and the SAS code can be found in Reference 4.

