The above primary analysis (Section 4.5.7) of the percentage of subjects with baseline HbA1c $\geq 7\%$ who achieve an HbA1c level < 7% at Week 26 between overall drug treatment (low-dose and high-dose) and placebo will be repeated with the difference that subjects with any baseline HbA1c value will be used. A logistic regression model will be used for this analysis.

4.5.7.2 Metformin subgroup analysis for comparison of percentage of subjects with baseline HbA1c $\geq 7\%$ who achieve an HbA1c level < 7% at Week 26 between overall drug treatment and placebo

The logistic regression model used for the primary analysis (Section 4.5.7) of the percentage of subjects with baseline HbA1c $\geq 7\%$ who achieve an HbA1c level < 7% at Week 26 between overall drug treatment (low-dose and high-dose) and placebo will also be repeated for the subgroup of subjects on a stable baseline dose of metformin IR or XR (with or without insulin). The same multiple imputation method used for the primary analysis of the endpoint will be used for this subgroup analysis. The indicator for background medication used in the multiple imputation step for insulin only and insulin with metformin will be grouped as defined in Section 4.1.12.

4.5.8 Comparison of the percentage of subjects with baseline HbA1c $\geq 7\%$ who achieve an HbA1c level < 7% at Week 26 between the low-dose/high-dose treatment regimen and placebo

Data will be multiply imputed based on the same approach as described for the primary analysis of the primary endpoint in Section 4.4.1, and will include all data regardless of rescue medication initiation or adherence. HbA1c response (< 7%) will be derived from dichotomising the imputed continuous values of HbA1c and Rubin's rules will be used to combine analyses across the multiple imputations. Estimates will be derived from a weighted logistic regression or Fisher's exact test (as appropriate) and combined as described in Section 4.1.12.4. The weight matrix W1 (described in Section 4.1.9) for the comparison of the low-dose/high-dose treatment regimen versus placebo will be used for this analysis.

4.5.8.1 Sensitivity analysis for secondary endpoint of percentage of subjects who achieve an HbA1c level < 7% at Week 26 between the low-dose/high-dose treatment regimen and placebo

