The above primary analysis (Section 4.5.8) of percentage of subjects with baseline HbA1c $\geq 7\%$ who achieve an HbA1c level < 7% at Week 26 between the low-dose/high-dose treatment regimen and placebo will be repeated with no restriction on baseline HbA1c values. A weighted logistic model will be used for this analysis.

4.5.8.2 Metformin subgroup analysis for comparison of percentage of subjects with baseline HbA1c \geq 7% who achieve an HbA1c level $<$ 7% at Week 26 between the low-dose/high-dose treatment regimen and placebo

The weighted logistic regression model used for the primary analysis (Section 4.5.8) of the percentage of subjects with baseline HbA1c \geq 7% who achieve an HbA1c level $<$ 7% at Week 26 between the low-dose/high-dose treatment regimen and placebo will also be repeated for the subgroup of subjects on a stable baseline dose of metformin IR or XR (with or without insulin). The same multiple imputation method used for the primary analysis of the endpoint will be used for this subgroup analysis. The indicator for background medication used in the multiple imputation step for insulin only and insulin with metformin will be grouped as defined in Section 4.1.12.

4.5.9 Comparison of the percentage of subjects with baseline HbA1c \geq 7% who achieve an HbA1c level $<$ 7% at Week 26 between the low-dose treatment regimen and placebo

Data will be multiply imputed based on the same approach as described for the primary analysis of the primary endpoint in Section 4.4.1, between the low-dose treatment regimen and placebo, and will include all data regardless of rescue medication initiation or adherence. HbA1c response ($<$ 7%) will be derived from dichotomising the imputed continuous values of HbA1c and Rubin's rules will be used to combine analyses across the multiple imputations. Estimates will be derived from logistic regression or Fisher's exact test (as appropriate) and combined as described in Section 4.1.12.4. The weight matrix W2 described in Section 4.1.9 for the comparison of the low-dose treatment regimen versus placebo will be used for this analysis.

4.5.9.1 Sensitivity analysis for secondary endpoint of percentage of subjects who achieve an HbA1c level $<$ 7% at Week 26 between the low-dose treatment regimen and placebo

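### Responder tests 7 and 8 count a weight-2 child as two children: with raw weights and few missing Week 26 values, the local level is about 7–9% and the 95% odds-ratio intervals cover about 90–92%

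*SAP*

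**What the plan says.** SAP 4.1.9 defines two weight sets. Under W1 (low-dose/high-dose regimen), a Week 12 non-responder re-randomised 1:1 to stay on the low dose gets weight 0, and one who "received the high-dose will be assigned a weight of 2". W2 (low-dose regimen) is the mirror image. Placebo children, Week 12 responders and children who are not re-randomised get weight 1.

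SAP 4.5.8 applies W1 to test 7: "Estimates will be derived from a weighted logistic regression". SAP 4.5.9 does the same for test 8: "The weight matrix W2 described in Section 4.1.9 for the comparison of the low-dose treatment regimen versus placebo will be used for this analysis".

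SAP 4.1.10 names SAS LOGISTIC as the procedure and states that "estimates, confidence intervals, and tests will be obtained using a weighted or unweighted logistic regression". The reported interval is the "Adjusted odd ratio and corresponding 95% Log likelihood confidence interval".

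For pooling, SAP 4.1.12.4 begins with "Obtain log-transformed odds ratio (OR) and SE from each imputed dataset", works the SE out from the interval limits, and adds that "The above code assumes that 95% CIs are used".

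Neither document mentions normalised weights, a robust variance or any other adjustment for the weighting. SAP 4.5.1 judges each secondary test at two-sided 0.05 and keeps reporting intervals and p-values after the sequence has stopped.

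**The concern.** The weights are sound for estimation: doubling the half that followed the regimen stands in for the half that did not. The difficulty is the variance. In a logistic likelihood the variance is fixed by the fitted probability, so raw weights act as frequencies. One weight-2 child is then treated as two independent observations.

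At stake are two odds ratios per drug. Their intervals would be labelled 95% but be too narrow, and their p-values would be too small. Both would be reported wherever the hierarchy stops. Not affected are the primary test and secondary tests 3, 6 and 9–11, which are unweighted. The weighted HbA1c and FPG tests (1, 2, 4 and 5) are outside this point.

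**Working it through.** **Inputs from the documents.** 81 per arm; SD of HbA1c change 1.7%; difference 0.75%; two-sided 0.05; 1:1 second randomisation; weights 0/1/2. The plan's power is reproduced: SE = 1.7 × √(2/81) = 0.267; 0.75/0.267 = 2.81; 2.81 − 1.96 = 0.85, which gives power 0.80.

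**Inputs assumed, because the documents give none.** Week 12 response share r 0.22–0.60; Week 12–26 correlation 0.4 or 0.8; baseline HbA1c normal(8.0, 1.2) truncated to 6.5–10.5%, so that 89% (about 72 per arm) have baseline ≥ 7%.

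**Hand check from W1.** In the active arm:
- Sum of weights: rn + 2 × (1−r)n/2 = n.
- Sum of squared weights: rn + 4 × (1−r)n/2 = n(2−r).
- Effective size: n²/[n(2−r)] = n/(2−r). At r = 0.33 this is 81/1.67, about 48, while the likelihood counts 81.
- Against unweighted placebo, the ratio of true to model SE is √((3−r)/2), and the level is 2[1 − Φ(1.96/ratio)].

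| r | SE ratio | Implied level |
|---|---|---|
| 0.22 | 1.18 | 9.6% |
| 0.33 | 1.16 | 9.0% |
| 0.60 | 1.10 | 7.4% |

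This ignores the lower outcome variance of Week 12 non-responders. A closed form that allows for it adds (1−r)p₂(1−p₂)/n (exact half split) or (1−r)[p₂(1−p)² + (1−p₂)p²]/n (free randomisation) to the active arm's model variance p(1−p)/n. Here p is the regimen's Week 26 response rate and p₂ that of Week 12 non-responders. Over r 0.10–0.50, p₂ 0.05–0.20 and Week 26 response 0.60–0.80 in Week 12 responders, the level is 5.6–9.8%.

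**Simulation, complete data.** W1 weights; logistic model with baseline HbA1c and strata main effects; baseline ≥ 7%; at least 5 responders per group; 10,000 replicates in each of 8 scenarios.

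| Method | Level (nominal 5%) |
|---|---|
| Raw weights, Wald | 7.2–9.0% |
| Raw weights, log-likelihood interval | 7.9–9.5% (coverage 90.5–92.1%) |
| Raw weights, SE from interval limits (3 scenarios of 3,000) | 7.4–8.1% |
| Sandwich variance | 4.8–5.9% |
| Weights rescaled to number of children | 4.1–6.4% |

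The ratio of true to model SE was 1.13–1.18. With a true effect (regimen odds ratio 2.1–2.4), the log-likelihood interval covered 89.6–91.4% and the sandwich interval 94.0–94.7%. A separate simulation at SD 1.7% with 60–75 children per arm gave Wald 7.2–8.8%, likelihood-ratio 8.2–9.6% and profile-interval coverage 90.4–91.8%. The unweighted test 6, run as a control, gave 4.8–5.7%.

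**Simulation, wash-out imputation.** r 0.22–0.45, correlation 0.6, 20 imputations (the SAP plans 200), Rubin pooling of Wald SEs.

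| Missing per arm | Raw weights | Sandwich | Rescaled |
|---|---|---|---|
| 2/81 = 2.5% | 7.0–7.7% | 4.2–4.7% | 3.9–5.3% |
| 4/81 = 4.9% | 6.0–7.0% | 3.8–4.6% | 3.8–4.7% |
| 8/81 = 9.9% | 4.3–5.2% | 2.6–3.5% | 2.4–3.9% |

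The separate simulation gave 8.3% at 2% missing, 6.0–6.4% at 5%, about 4.5% at 10% and about 2.5% at 20%, all with raw weights.

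**Printed SE formula (SAP 4.1.12.4).** For an interval of 0.5–2.0, as printed: log 2 − (log 0.5)/3.92 = 0.693 + 0.177 = 0.870. With the bracket: (log 2 − log 0.5)/3.92 = 1.386/3.92 = 0.354.

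**The case against.** **Reach.** Tests 7 and 8 come after the primary test and tests 1–6, and test 6 is the same endpoint unweighted. In a simulation with no effect on response, tests 6 and 7 both rejected in only 3.0–3.8% of trials, before requiring the primary and tests 1–5. This stands, and no family-wise excess is claimed. It does not repair the intervals, which are reported in any case.

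**Missing data.** The excess is mostly gone at 5% missing and absent at 10%, and the plan prepares for drop-out and pandemic-affected visits. The current text gives no expected rate. The only figure, 2%, is in sample-size text deleted by Amendment 06. The size is therefore conditional. But the sandwich's 2.6–3.5% at 9.9% missing shows that wash-out imputation with Rubin pooling is itself conservative, so near-nominal raw weights there reflect two errors cancelling. SAP 4.1.10 also provides for fitting without imputation when nothing is missing.

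**Assumed response rates.** Lower response reduces the excess. Settings with SD 1.0–1.3 or a high baseline gave Wald levels of 4.2–7.0%, partly because many such trials fail the 5-responder rule and go to Fisher's test. Results at a baseline mean of 8.5 differ: one check gave 6.6%, and 5.4% with SD 1.3. Another, covering baseline means 8.0 and 8.5 and SDs 1.3 and 1.7, gave Wald 7.3–8.4% throughout. This limits the size, not the mechanism.

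**Raw weights are inferred.** The SAP names the procedure but not its weight option, and output specifications are in separate documents. That is true. An unstated option that decides between about 8% and about 5% belongs in the SAP. The weighted proportion in SAP 4.1.3, "the weighted count of subjects with the event out of the total number of weighted subjects in the analysis set", is a correct descriptive definition and says nothing on variance either way.

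**Not covered.** The SAP's preferred retrieved drop-out imputation was not simulated. At r = 0.3, the chance that both weight-2 cells of a drug reach the required 5 is 0.02, 0.17 and 0.47 if 10%, 15% and 20% of children are retrieved drop-outs (assumed rates).

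**Conclusion.** The concern holds. As written, the variance for tests 7 and 8 is wrong, not merely underspecified. With raw weights, an SD of 1.7% and up to about 2–3% missing Week 26 values, the local level is about 7–9%. In complete data the nominal 95% odds-ratio intervals cover about 90–92%. The excess is about 1–2 points near 5% missing and nil near 10%.

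The size rests on assumed response rates, baseline distribution and Week 12–26 correlation, and on 81 per arm, which excluding Site 4910 (SAP 4.10) may lower. Simulations used W1; W2 mirrors it. The missing bracket is a separate, confirmed error that would distort every pooled responder SE if coded literally. This should be fixed, but it does not touch the primary conclusion.

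**What to change.** For tests 7 and 8, keep the weights, estimand and hierarchy, and state the variance: a robust (sandwich) variance with the subject as unit, for example SURVEYLOGISTIC or GENMOD with a REPEATED statement. Take the log odds ratio and its SE directly from that fit and pool by Rubin's rules. If the SE is still derived from interval limits, add the bracket in SAP 4.1.12.4.

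A smaller change is to state that LOGISTIC weights are rescaled to the number of children used (NORMALIZE). It removes most of the excess but is not exact. The children with positive weight number n + n(1+r)/2 against a weight total of 2n, a factor of (3+r)/4. At r = 0.33 that is 0.8325, so the SE rises by 1/√0.8325 = 1.10, where the hand check needs 1.16.

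Using the robust option for tests 1, 2, 4 and 5 as well is optional, for consistency.

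The cost is SAP wording and one procedure option. Responder SEs grow by about 10–14% on average in complete data. Near 10% missing the robust test becomes conservative (2.6–3.5%, against 4.3–5.2% for raw weights).
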